##### ***Data management:***

Electronic Case Report Forms reside on a secure server that is regularly backed up. Data is entered manually by keyboard in the Research Stools Database. All participants have unique screening and randomisation numbers. Participant personal details (name, DOB etc) are de-identified in each record but are linkable via the allocated screening number.

Data input has range checks for most variables. Double data entry will be used for all outcomes that require manual keyboard entry.

The investigator team will have access to the final trial dataset. Any other persons would require approval from the investigator team.

All data will be stored securely for at least 15 years.

##### ***Data Analysis:***

Outcome data will be analysed using Linear Mixed Model Analysis of variance due to expected inter-patient variability and repeated measures. Patients will be random

factors. Treatment and time (0 & 3 months) will be fixed factors. The Treatment x Time interaction will be examined to see the specific difference between treatments at just the 3 month time point. Analysis will be by intention to treat and will include all participants who are randomised at 0 months including drop-ins to CPAP and participants who do not adhere to treatment.

Exploratory mixed models analyses of OSA severity accounting for CPAP compliance and weight change will also be conducted using 12 month followup data.

**Data Monitoring:** As all treatments are routinely applied in clinical care, a Data Monitoring Committee will not be appointed. Instead, all adverse events and serious adverse events will be monitored by the investigating team and discussed at regular monthly meetings. Patients who develop excessive sleepiness in the weight loss alone arm will be assessed by the study sleep physicians to determine the cause of the sleepiness and be considered on a case-by-case basis for being placed on CPAP therapy. Side effects attributable to the VLED will be managed by the dietician in consultation with the endocrinology/metabolic physician team.

There are no planned interim analyses. The final decision to terminate the trial lies with the Principal Investigators. Stopping guidelines will be based on (1) safety data and (2) ongoing trial funding. The investigators will conduct a 6 monthly review of all SAEs (pre-defined on page 22) and if after discussion the rate of SAE's is deemed unacceptable by the PI's then the study will be stopped and the HREC will be advised of the decision.

Internal procedures for monitoring trial conduct will be followed. Where available an external monitor will be engaged.

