## ***1.5 Outline of the Proposed Research***

***Project Title:*** Cardio-metabolic health effects of CPAP treatment for sleep apnoea during weight loss: A Randomised Controlled Pilot Trial

***Objective:*** To determine in obese people with pre-diabetes, the efficacy of treating OSA with CPAP during weight loss, to achieve greater improvements in glucose tolerance (a measure of diabetes risk), abdominal fat loss and other cardio-metabolic measures at three months. All patients will be invited to attend a follow up visit at 12 months with reassessment of outcomes, after following a low glycaemic index (GI)/high protein diet and exercise program for nine months.

***Design:*** A three month Randomised Controlled Trial (RCT) in obese pre-diabetic patients with OSA randomised to a very low energy diet (VLED) (control) or CPAP plus VLED (intervention). Following the randomised controlled phase, patients will be re-assessed for OSA severity. Any patients with persistent OSA will commence or continue on CPAP treatment if recommended by their treating sleep physician. In addition, all patients will receive education about how to maintain a healthy weight using a low GI/high protein diet and exercise program. Optional support from a dietitian will be offered. All patients will be invited to attend a follow up visit at 12 months with reassessment of outcomes.

***Hypotheses:*** Treatment of OSA with CPAP during a VLED, compared with a VLED alone for three months, will better improve:

1. Glucose tolerance and HbA1c
2. Central Blood Pressure
3. Abdominal and total fat mass
4. Lipid profiles

***Patients:*** Female and male centrally or generally obese adults with pre-diabetes and moderate-severe OSA.

***Primary Outcome:*** Glucose tolerance, as measured by two hour blood glucose level following an oral glucose tolerance test, assessed at three months.

**Secondary Outcomes:** Abdominal and body fat, metabolic syndrome components (glucose, lipids, BP), insulin sensitivity, 24 hour blood glucose levels, 24 hour central blood pressure, health related quality of life and cost effectiveness measures.

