### 2.2 Inclusion / Exclusion Criteria

#### **Inclusion**

1. Community dwelling adults aged 18-65 years
2. Body Mass Index (BMI):  $\geq 27 \text{ kg/m}^2$  and/or waist circumference: females  $>88\text{cm}$ , males  $>102\text{cm}$  (non-European: females  $>80\text{cm}$ , males  $>90\text{cm}$ )
3. Pre-diabetes defined per World Health Organisation as any of the following recent ( $<3$  months) findings:
  - Impaired fasting glucose with BGL between 5.5 and 7.0 mmol/L
  - Impaired glucose tolerance with BGL between 7.8 and 11.0 mmol/L after a formal 75g Oral Glucose Tolerance Test (OGTT)
  - HbA1C between 6 and 6.5%
4. Moderate-severe hypoxaemic OSA with  $\text{AHI} \geq 20/\text{hr}$  and  $\text{ODI} \geq 10/\text{hr}$  prior to VLED, based on recent ( $<12$  months) polysomnography

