### ***3.2 Enrolment and Randomisation to Treatment***

Only eligible adults providing written informed consent, according to the protocol approved by the local ethics committee, will be enrolled into the trial.

Patients will be enrolled sequentially according to the randomisation list. After screening and baseline assessment, all participants will be randomised in a 1:1 ratio into either:

1. CPAP + VLED (Intervention) OR
2. VLED alone (Control)

This is an open label study; it is not possible to blind the study due to the nature of CPAP treatment.

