#### ***4 Statistical Methods***

##### ***Sample Size:***

30 patients will be required to complete the randomised phase of this pilot study. Allowing for an approximate 20% dropout, n=38 will need to be randomised.

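### The Treatment x Time interaction is described as the 3-month difference, but as modelled it is the difference in change from baseline; a baseline-adjusted 3-month difference would match the description and usually be more precise

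*Protocol*

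**What the plan says.** Section 1.5 of the protocol defines the primary outcome as "Glucose tolerance, as measured by two hour blood glucose level following an oral glucose tolerance test, assessed at three months". The hypothesis in the same section is worded as improvement: CPAP during a VLED, "compared with a VLED alone for three months, will better improve" glucose tolerance and the other listed outcomes.

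Section 4, Data Analysis, specifies a linear mixed model. "Treatment and time (0 & 3 months) will be fixed factors", and patient is the random factor. The tested term is then named and interpreted: "The Treatment x Time interaction will be examined to see the specific difference between treatments at just the 3 month time point". No baseline covariate is mentioned, nor any constraint that the arms share a baseline mean.

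On timing, section 3.2 states: "After screening and baseline assessment, all participants will be randomised in a 1:1 ratio into either" arm. On size, section 4 states: "30 patients will be required to complete the randomised phase of this pilot study", with 38 randomised to allow for about 20% dropout.

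**The concern.** The sentence on the interaction joins two quantities that are not the same. In a model with treatment, two time points and their interaction, the interaction is the between-arm difference in change. The difference at 3 months is the month-0 treatment effect plus the interaction. A reader who follows the named term reports one number, and a reader who follows the description reports another. In an open-label trial of this size the gap may be large enough to see, and the choice could then be made after the data are known.

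The second issue is precision. A change contrast subtracts the whole chance baseline difference, although only part of it predicts the 3-month value. Baseline 2-hour glucose is already measured in everyone before allocation, so a more efficient use of it is available.

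**Working it through.** **Inputs.** Model, tested term, 30 completers and 38 randomised: section 4. Baseline before 1:1 randomisation: section 3.2. OGTT at 0 and 3 months: section 3.7 (Visits 2 and 7) and Appendix A. From these, 15 completers and 19 randomised per arm. The protocol gives no SD, no baseline to 3-month correlation (ρ) and no significance level. I assume equal SDs at both times, ρ from 0.3 to 0.9, and two-sided 5% where an interval is needed. Results are in SD units.

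**The plan's own figure.** 30 / (1 − 0.20) = 37.5, rounded up to 38. This reproduces. (Section 2.1 gives 30 as the number randomised; I follow section 4.)

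**Step 1: what the interaction is.** Let τ be the arm difference at month 0 and δ the interaction. The 3-month difference is τ + δ, and the difference in change is (τ + δ) − τ = δ. A mixed model of this form, fitted to one simulated trial of 30 patients, gave an interaction of 0.320, equal to the difference in mean change. The 3-month difference was 0.045 and the chance baseline difference −0.276; 0.045 + 0.276 = 0.321, which agrees up to rounding.

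**Step 2: bias.** Randomisation after baseline makes the expected value of τ zero, so the two contrasts have the same expectation. In 20,000 simulated null trials at each of ρ = 0.3, 0.5 and 0.7, the mean interaction, 3-month difference and adjusted difference were all within 0.005 SD of zero.

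**Step 3: chance imbalance.** The standard error of the baseline difference is √(2/15) = 0.37 SD. An imbalance of that size separates the interaction from the raw 3-month difference by 0.37 SD. It separates the interaction from the adjusted estimate by (1 − ρ) × 0.37, which is 0.18 SD at ρ = 0.5.

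**Step 4: precision.** Up to the common factor 2/15, the interaction has variance 2(1 − ρ) and the baseline-adjusted estimate 1 − ρ². The ratio is (1 + ρ)/2. Two refinements:

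- *ANCOVA in 30 completers.* Estimating the slope inflates variance by 1 + 1/(30 − 4) = 1.038, and moving from 28 to 27 degrees of freedom multiplies it by a further 1.003. The combined factor is 1.042.
- *Mixed model, 19 randomised and 15 completing per arm, covariance taken as known.* With free baseline means the variance is 2[(1 − ρ²)/15 + (1 − ρ)²/19]. With one shared baseline mean it is 2(1 − ρ²)/15. At ρ = 0.5 these are 0.1263 and 0.1000, a ratio of 0.79.

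| ρ | (1 + ρ)/2 | ANCOVA, corrected | Shared baseline, 38/30 | 95% CI half-width, 30 completers: interaction / ANCOVA |
|---|---|---|---|---|
| 0.3 | 0.65 | 0.68 | 0.70 | 0.89 / 0.73 |
| 0.5 | 0.75 | 0.78 | 0.79 | 0.75 / 0.66 |
| 0.7 | 0.85 | 0.89 | 0.88 | 0.58 / 0.55 |
| 0.9 | 0.95 | 0.99 | 0.96 | 0.33 / 0.33 |

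The simulated standard errors agree (interaction / adjusted): 0.430 / 0.357, 0.366 / 0.323 and 0.283 / 0.266 at ρ = 0.3, 0.5 and 0.7. Because 2(1 − ρ) exceeds 1 when ρ is below 0.5, the interaction is then less precise than a comparison that ignores baseline. ANCOVA stops gaining at ρ of about 2/1.042 − 1 = 0.92.

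**The case against.** The strongest reply is that the planned test is valid. Its expectation is right, and it answers a hypothesis worded as better improvement. This stands in full. A reader might infer from the mislabelled contrast that the analysis is biased or tests the wrong hypothesis; the documents do not support that, and no bias is alleged.

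A second reply is that free baseline means are inferred from the listed factors, and that an SAP could constrain the baseline. If the arms shared a baseline mean, the interaction would indeed be the 3-month difference. But section 4 lists treatment as a fixed factor without such a constraint. One could also read the sentence as taking the month-3 contrast from the fitted cell means. The tested term would then not be the interaction, and with complete data the contrast would have a half-width of 0.75 SD at every ρ. Either way the sentence needs correcting, and neither reading uses baseline efficiently.

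A third reply concerns size, and it also stands. The gain depends on a ρ that the protocol does not give, on equal SDs, and is almost gone by ρ = 0.9. ANCOVA is not entirely free: it costs one degree of freedom and about 4% in variance. This is also a pilot with no stated power, so no promised operating characteristic is missed.

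It is also tempting to argue that entry on any one of three glycaemic criteria in section 2.2 makes regression to the mean strong. That does not follow. For a given measurement error, a wider true spread raises ρ and weakens regression to the mean, and patients entering on fasting glucose or HbA1c are not selected on 2-hour glucose. The point does not rely on it.

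**Conclusion.** The description in section 4 is wrong for the model that it describes: the interaction is a difference in change, not the difference at 3 months. This part needs no assumption beyond the listed factors. The planned analysis remains unbiased and valid for the hypothesis, so this is a correction of the stated estimate together with an available gain in precision, not a failure of the test.

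The gain is useful at low to moderate correlation and negligible at high correlation. Dividing 30 by the unrounded ANCOVA ratios (0.677, 0.781, 0.886 and 0.990), the interaction would need about 44, 38, 34 or 30 completers to match ANCOVA in 30, at ρ = 0.3, 0.5, 0.7 or 0.9. These figures rest on equal SDs at 0 and 3 months; unequal SDs would move them in either direction. The mixed-model ratios also treat the covariance as known.

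**What to change.** Replace the interaction sentence in section 4 with: *The primary estimate is the CPAP+VLED minus VLED difference in 2-hour glucose at 3 months, adjusted for baseline 2-hour glucose, with 95% CI.*

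Fit it preferably as the planned mixed model with the treatment effect at month 0 removed, so that both arms share one baseline mean. This has one mean parameter fewer than the planned model, and it keeps every randomised patient with a baseline value, in line with the intention-to-treat statement. (In the calculation above, the baseline-only patients do not sharpen the contrast; the reason to keep them is the analysis population.) ANCOVA of the 3-month value on treatment and baseline is an acceptable alternative, at a cost of one degree of freedom.

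Use the same form for the other continuous outcomes measured at 0 and 3 months. The cost is one sentence in the protocol and a matching line in any SAP, with no new data and no added burden on patients.

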***Dissemination:***

Findngs will be disseminated via conferences, publications and media, as applicable. Patients will be informed of results of the study at the conclusion of the trial. Eligible authors will include investigators who are involved in the conception and design of the study, the conduct of the trial, the analysis of the results and authorship and

presentation of study findings. The full protocol will be added to the ANZCTR registry.

Appendix A: Time Frame for Study Visits	Visit number	2	3	4	5	6	7	8	9	10	11
	Month	0	1W	2W	1M	2M	3M	5M	7M	9M	1Y
Study Phase	Screen	Randomised Controlled					Follow up (optional consultations)				
Lifestyle Modification Phase		Very Low Energy Diet (VLED)				Trans- -ition	Low GI/High Protein Diet				
CPAP Phase		Randomised to CPAP or No CPAP					Usual Care for CPAP				
Eligibility & Informed Consent	X										
Randomisation to CPAP		X									
Reassessment of OSA and transfer into follow up phase with optional support							X				
Glucose Tolerance (OGTT, MINMOD)		X					X				X**
Total Body Fat & Lean Mass (DXA) & Bioimpedence		X					X				X
Anthropometry, Vitals		X			X	X	X				X
Blood Markers (Lipids,HbA1c,IGF1,IGFBP1)		X					X				X
24 Hour Testing (Continuous Central Blood Pressure & Continuous Glucose Monitoring)		X					X				X
4-day Food Diary		X						X			X
24-hr Food Recall					X	X	X		X	X	
Questionnaires		X					X				X
Sleep Study	X						X				X*
Lifestyle Consultation		X			X	X	X		X		X
Lifestyle Support Call			X	X				X		X	

\* PSG if clinically indicated by symptoms of obstructive sleep apnoea

\*\* If clinically indicated by elevated fasting blood glucose result

## Appendix B – Schedule of Participant visits

Screen (Visit 1)	
 
• Woolcock screen visit with physician and study coordinator to assess study eligibility
 
• Issue 4-day food diary
 
• Includes overnight sleep study if not conducted within preceding 12 months to confirm OSA severity
 

Baseline (Visit 2)	
 
• Full Assessment including dietary and exercise assessment and all other study procedures listed during a half day clinic visit
 
• Measurement of glucose tolerance, insulin sensitivity, total body fat and lean mass
 
• Measurement of anthropometry, vitals, metabolic blood markers
 
• Assessment of food diary and education on VLED diet
 
• Complete diet, exercise and quality of life questionnaires
 
• Issue VLED shakes – Stage 1
 
• 24 hour central blood pressure monitoring and 24 hour continuous blood glucose monitoring
 

1 week (Visit 3)	
 
• Phone call or Skype contact lasting 15-30minutes
 
• Emphasis: VLED compliance and safety
 

2 weeks (Visit 4)	
 
• Phonecall or Skype contact lasting 15-30 minutes
 
• Emphasis: VLED compliance and safety
 

1 month (Visit 5)	
 
• 2 hour clinic session
 
• Anthropometry & vitals
 
• 24 hour recall
 
• Session: Exercise, Planning, Doing, Tracking
 

2 month (Visit 6)	
 
• 2 hour clinic session
 
• Anthropometry & vitals
 
• Education on Low GI/High Protein Diet and transition phase diet
 

3 month (Visit 7)	
 
• Full Assessment including dietary and exercise assessment and all other study procedures listed during a half day clinic visit
 
• Sleep study performed one week after Visit 7. Those using CPAP will have a one week washout prior to sleep study
 
• Measurement of glucose tolerance, insulin sensitivity, total body fat and lean mass
 
• Blood test, body measurements, bioelectrical impedance analysis, blood pressure, heart rate, wrist accelerometer and sensewear & diary and lifestyle consultation
 
• 24hr food recall
 
• 24 hour central blood pressure monitoring and 24 hour continuous blood glucose monitoring
 
•
 

5 month (Visit 8)	
 
• 2 hour clinic session OR Phone call/ Skype lasting 30- 60
 

– optional	
minutes
 
 
• Clinical assessment involving: anthropometry and vitals, bio-impedance spectroscopy, questionnaires and lifestyle consultation
 
• Session: Headspace and Food Choices
 
• 4 day food diary
 

7 month (Visit 9) – optional	
 
• Phone call or Skype lasting 30- 60 minutes
 
• 24 hour food recall
 
• Lifestyle consultation
 

9 month (Visit 10) – optional	
 
• Phone call or Skype lasting 15 - 30 minutes
 
• Session: Maintaining the Change
 

12 month (Visit 11) – optional	
 
• Full Assessment including dietary and exercise assessment and all other study procedures listed during a half day clinic visit
 
• Sleep study for those clinically indicated
 
• Measurement of fasting blood glucose (and glucose tolerance/ insulin sensitivity if clinically indicated), total body fat and lean mass
 
• Blood test, body measurements, bioelectrical impedance analysis, and lifestyle consultation.
 
• 24 hour central blood pressure monitoring and 24 hour continuous blood glucose monitoring
 
• 4 day food diary completed
 
• Study complete
 

## Appendix C: Concomitant Medications

Were any medications, including over-the-counter and health/dietary supplements, taken by the patient during the study?

Yes → Enter information on this sheet.  No

Line #	Name of Medication	Dose	Units	Freq	Route	Indication If med. taken due to AE, record AE # →	AE #	Date		Ongoing at end of study?
								Start	End	
1								Start		
								End		
2								Start		
								End		
3								Start		
								End		
4								Start		
								End		
5								Start		
								End		
6								Start		
								End		
7								Start		
								End		

## Appendix D: Risk Stratification

### ADULT PRE-EXERCISE SCREENING TOOL

This screening tool does not provide advice on a particular matter, nor does it substitute for advice from an appropriately qualified medical professional. No warranty of safety should result from its use. The screening system in no way guarantees against injury or death. No responsibility or liability whatsoever can be accepted by Exercise and Sports Science Australia, Fitness Australia or Sports Medicine Australia for any loss, damage or injury that may arise from any person acting on any statement or information contained in this tool.

Name: \_\_\_\_\_

Date of Birth: \_\_\_\_\_ Male  Female  Date: \_\_\_\_\_

#### STAGE 1 (COMPULSORY)

AIM: to identify those individuals with a known disease, or signs or symptoms of disease, who may be at a higher risk of an adverse event during physical activity/exercise. This stage is self administered and self evaluated.

Please circle response

1. Has your doctor ever told you that you have a heart condition or have you ever suffered a stroke?	Yes	No
2. Do you ever experience unexplained pains in your chest at rest or during physical activity/exercise?	Yes	No
3. Do you ever feel faint or have spells of dizziness during physical activity/exercise that causes you to lose balance?	Yes	No
4. Have you had an asthma attack requiring immediate medical attention at any time over the last 12 months?	Yes	No
5. If you have diabetes (type I or type II) have you had trouble controlling your blood glucose in the last 3 months?	Yes	No
6. Do you have any diagnosed muscle, bone or joint problems that you have been told could be made worse by participating in physical activity/exercise?	Yes	No
7. Do you have any other medical condition(s) that may make it dangerous for you to participate in physical activity/exercise?	Yes	No

▶
 IF YOU ANSWERED 'YES' to any of the 7 questions, please seek guidance from your GP or appropriate allied health professional prior to undertaking physical activity/exercise

▶
 IF YOU ANSWERED 'NO' to all of the 7 questions, and you have no other concerns about your health, you may proceed to undertake light-moderate intensity physical activity/exercise

I believe that to the best of my knowledge, all of the information I have supplied within this tool is correct.

Signature \_\_\_\_\_ Date \_\_\_\_\_

## Appendix E: Questionnaires

### Epworth Sleepiness Scale (ESS)

Imagine yourself in the following situations, and rate your chance of dozing or falling asleep within the last two weeks. Even if you do not find yourself in the situation (eg driving), imagine how they would have affected you. Indicate your answer by putting a tick "✓" in the appropriate box.

Situations	Chance of Dozing			
	Would never doze 0	Slight chance of dozing 1	Moderate chance of dozing 2	High chance of dozing 3
1. Sitting and reading				
2. Watching TV				
3. Sitting, inactive in a public place (e.g., a theatre or a meeting)				
4. As a passenger in a car for an hour without a break				
5. Lying down to rest in the afternoon when circumstances permit				
6. Sitting and talking to someone				
7. Sitting quietly after lunch without alcohol				
8. In a car, while stopped for a few minutes in the traffic				
Total score				

SIGNATURE: \_\_\_\_\_

DATE: \_\_\_\_\_

## Functional Outcomes of Sleep Questionnaire (FOSQ)

*Note:* In this questionnaire the words "sleepy" or "tired" are used, it describes the feeling that you can't keep your eyes open, your head is droopy, that you want to nod off or that you feel the urge to take a nap. These words do not refer to the tired or fatigued feeling you may have after you have exercised.

FOSQ questions are answered using numbers from 0-4.

- 0 = I don't do this activity for other reasons
- 1=Yes, extreme
- 2=Yes, moderate
- 3=Yes, a little
- 4=No

	I don't do this activity	Extremely	Moderately	A little	No
Q1 - Do you generally have difficulty concentrating on the things you do because you are sleepy or tired ?	 0	 1	 2	 3	 4
Q2 - Do you generally have difficulty remembering things because you are sleepy or tired ?	 0	 1	 2	 3	 4
Q3 - Do you have difficulty finishing a meal because you become sleepy or tired ?	 0	 1	 2	 3	 4
Q4 - Do you have difficulty working on a hobby (for example: sewing, collecting, gardening) because you are sleepy and tired?	 0	 1	 2	 3	 4
Q5 - Do you have difficulty doing work around the house (for example: cleaning house, doing laundry, taking out the trash, repair work) because you are sleepy or tired?	 0	 1	 2	 3	 4
Q6 - Do you have difficulty operating a motor vehicle for short distances ( less than 100 miles) because you become sleepy or tired?	 0	 1	 2	 3	 4
Q7 - Do you have difficulty operating a motor vehicle for long distances ( greater than 100 miles) because you become sleepy or tired?	 0	 1	 2	 3	 4
Q8 - Do you have difficulty getting things	 0	 1	 2	 3	 4

done because you are too sleepy or tired to drive or take public transportation?					
Q9 - Do you have difficulty taking care of financial affairs and doing paperwork (for example: writing checks, paying bills, keeping financial records, filling out tax forms , etc.) because you are sleepy or tired.	 0	 1	 2	 3	 4
Q10 - Do you have difficulty performing employed or volunteer work because you are sleepy or tired?	 0	 1	 2	 3	 4
Q12 - Do you have difficulty visiting with your family or friends in your home because you become sleepy or tired?	 0	 1	 2	 3	 4
Q13 - Do you have difficulty visiting your family or friends in their home because you become sleepy or tired?	 0	 1	 2	 3	 4
Q14 - Do you have difficulty doing things for your family or friends because you are too sleepy or tired?	 0	 1	 2	 3	 4
Q15 - For question 15 answer using only 1,2,3 or 4. Has your relationship with family, friends or work colleagues been affected because you are sleepy pr tired?	 0	 1	 2	 3	 4
Q16 - Do you have difficulty exercising or participating in a sporting activity because you are too sleepy or tired?	 0	 1	 2	 3	 4
Q17 - Do you have difficulty watching movie or videotape because you become sleepy or tired?	 0	 1	 2	 3	 4
Q18 - Do you have difficulty enjoying the theatre or a lecture because you become sleepy or tired?	 0	 1	 2	 3	 4
Q19 - Do you have difficulty enjoying a concert because you become sleepy or tired?	 0	 1	 2	 3	 4
Q20 - Do you have difficulty watching television because you are sleepy or tired?	 0	 1	 2	 3	 4
Q21 - Do you have difficulty participating in religious services, meetings or a group or club because you are sleepy or tired?	 0	 1	 2	 3	 4

Q22 - Do you have difficulty being as active as you want to be in the evening because you are sleepy or tired?	 0	 1	 2	 3	 4
Q23 - Do you have difficulty being as active as you want to be in the morning because you are sleepy or tired?	 0	 1	 2	 3	 4
Q24 - Do you have difficulty being as active as you want to be in the afternoon because you are sleepy or tired?	 0	 1	 2	 3	 4
Q25 - Do you have difficulty keeping pace with others your own age because you are sleepy or tired?	 0	 1	 2	 3	 4
Q26 - For question 26, answer only using the scale 1 = very low, 2=low, 3=medium, 4= high. How would you rate your general activity?	 0	 1	 2	 3	 4
Q27 - Has your intimate or sexual relationship been affected because you are sleepy or tired?	 0	 1	 2	 3	 4
Q28 - Has your desire for intimacy or sex been affected because you are sleepy or tired?	 0	 1	 2	 3	 4
29 - Has your ability to become sexually aroused been affected because you are sleepy or tired?	 0	 1	 2	 3	 4
Q30 - Has your ability to have an orgasm been affected because you are sleepy or tired?	 0	 1	 2	 3	 4

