### ***Questionnaires***

The following questionnaires will be completed at 0, 3 and 12 months:

1. The Epworth Sleepiness Scale (ESS)
2. Functional Outcomes of Sleep Questionnaire (FOSQ)
3. Depression, Anxiety and Stress Scales (DASS)
4. Impact of Weight on Quality of Life questionnaire (IWQOL)
5. International Physical Activity Questionnaire (IPAQ)

All questionnaires can be found in Appendix E

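### The FOSQ form printed in Appendix E skips item number 11, prints a 0 box that Q15 and Q26 do not allow, and sets Q26 under headings that read against its own scale

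*Protocol*

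**What the plan says.** Protocol section 3.8 (Questionnaires) lists the FOSQ second of five instruments to be completed at 0, 3 and 12 months and refers to Appendix E for all of them, so the Appendix E form is the one in use. Health-related quality of life is among the secondary outcomes in sections 1.5 and 3.1.

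The form opens with a general rule, "FOSQ questions are answered using numbers from 0-4", and a key in which 1 is extreme difficulty and 4 is none. The lowest code is defined as "0 = I don't do this activity for other reasons". Column headings follow the same order: a not-done column for 0, then Extremely (1), Moderately (2), A little (3) and No (4).

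Three places depart from this:

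- **Numbering.** The row "Q10 - Do you have difficulty performing employed or volunteer work because you are sleepy or tired" is followed directly by "Q12 - Do you have difficulty visiting with your family or friends in". The last row is "Q30 - Has your ability to have an orgasm been affected because you are sleepy or tired".
- **Q15.** Its text says "For question 15 answer using only 1,2,3 or 4", but the row prints boxes 0 to 4.
- **Q26.** It asks for a rating of general activity and says "For question 26, answer only using the scale 1 = very low, 2=low, 3=medium, 4= high". Its row also prints boxes 0 to 4, and no separate headings are given for it.

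**The concern.** These are faults in the form itself, so they act when the data are collected. An analysis plan can say how to score the answers, but it cannot restore a question that was never asked. Nor can it tell whether a patient ticked Q26 by the written scale or by the column heading.

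Section 4 (Data management) provides range checks for most variables and double entry of manually keyed outcomes. A range check set to 1-4 would stop a 0 at Q15 or Q26. It would not stop a misread Q26, because the wrong answer is still within 1-4. Double entry would copy the wrong tick faithfully. With 30 completers planned (section 4, Sample Size), a few misread forms have little room to average out.

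At stake is the completeness and coding of one sleep-specific questionnaire, not the trial's main conclusion.

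**Working it through.** The protocol states no figure to reproduce here. It gives neither an item count nor a scoring rule for the FOSQ. The check is a count and a comparison of each instruction with its boxes.

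**1. Item count.** Printed rows are Q1-Q10 (10 items) and Q12-Q30 (30 − 12 + 1 = 19 items), so 10 + 19 = 29. The numbers run to 30 and only 11 is absent: 1/30 = 3.3% of the numbers.

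**2. Omitted item or numbering slip?** Two later items name their own number in their wording (Q15 and Q26), and both match their row labels. Had the rows been numbered wrongly from 11 on, those self-references would be expected to disagree with the labels. An omitted row is therefore the likelier explanation.

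**3. The 0 box.**

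| Item | Own instruction | Boxes printed |
|---|---|---|
| Q15 | 1-4 only | 0-4 |
| Q26 | 1-4 only | 0-4 |

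Each row offers an answer that its own text rules out.

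**4. Q26 headings against Q26 codes.**

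| Box | Printed heading | Q26's own meaning |
|---|---|---|
| 1 | Extremely | very low |
| 2 | Moderately | low |
| 3 | A little | medium |
| 4 | No | high |

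On the common key a higher number means better function. On Q26 a higher number means more activity. The codes run the same way, so no reverse scoring is involved; only the heading words read the other way.

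**5. Size of a misreading.** Let *a* be the patient's true level on Q26 (1 to 4). Someone who answers by heading ticks box 5 − *a*, so the error is (5 − *a*) − *a* = 5 − 2*a*:

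- *a* = 1: +3
- *a* = 2: +1
- *a* = 3: −1
- *a* = 4: −3

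The largest error at one completion is 3 points on the item. Assuming a simple unweighted mean of the 29 printed items, that is 3/29 = 0.10. The sign depends on the true level, so errors partly cancel across patients of differing activity.

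A patient who misreads the item at both 0 and 3 months has the direction of the Q26 change flipped. A true one-step rise becomes a one-step fall, an error of 2 points, or 2/29 = 0.07 on the same assumed mean.

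**6. Who is affected.** A patient who follows the printed instruction at Q15 and Q26 gives a correctly coded answer. The protocol offers no basis for the proportion who would not, so the figures in step 5 are upper limits per patient and not expected biases.

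**The case against.** The strongest reply is that much of this cannot be settled from the protocol. It never says how many items the FOSQ should have, and the questionnaire table is visibly broken in the text available (Q8 is split around its boxes), so row 11 may have been lost in reading the PDF. The headings appear only once, above Q1, and a repeated header nearer Q26 could have been lost too. Q26 states its own scale and each box carries its number. Both arms use the same form, the FOSQ is one of five questionnaires, and the 12-month visit is optional.

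Most of this stands, and it limits the size of the point. It does not remove it. Q10 and Q12 are adjacent rows away from the visible break at Q8, and the self-naming items fit an omission better than a slip, although loss in PDF reading cannot be excluded. The 0 boxes contradict the text of their own rows wherever the headings fall.

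Three stronger readings are tempting and are not supported:

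- *Q26 is scored in the reverse direction.* It is not; only the headings read backwards.
- *The FOSQ score would be wrong as collected.* Patients who follow the instructions are coded correctly, and without the source instrument the missing number is an apparent omission, not a proven one.
- *A 0 would enter the sum as worse than extreme difficulty.* The protocol has no rule that does this. The key defines 0 as a not-applicable label, and its handling may properly be left to the SAP, which was not at hand.

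**Conclusion.** The form contradicts itself and should be corrected, but the fault is minor. One item appears to be omitted (29 printed under numbers 1 to 30), two items offer an answer that their own wording forbids, and Q26 is open to misreading by anyone who goes by the headings. The FOSQ score may therefore be incomplete. A misread Q26 costs at most 3 points on that item at one completion, about 0.10 on the mean.

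The 0.10 rests on an assumed unweighted 29-item mean. The omission rests on the numbering as it appears in the available text. The Q26 effect rests on some patients answering by heading, at a rate the protocol does not let us estimate. The primary outcome and the sample size are unaffected. With the same form in both arms, the likely consequence is noise or some loss of sensitivity in one secondary measure.

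**What to change.** In Appendix E, before the form is used:

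1. Compare the form with the source instrument and restore item 11 if it was omitted. If the number is skipped there too, say so in a note.
2. Print Q26 with its own headings: very low, low, medium, high.
3. Remove the 0 box from Q15 and Q26.
4. Limit both items to 1-4 in the study database.

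If forms have already been completed, record which version each patient used at each visit, so that the analysis can identify scores from the uncorrected form.

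The cost is a corrected page and two database range checks. No visit, assessment or staff time is added for patients.
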